### CONFIDENTIAL

# **1.3.2.** Assessment Schedule Example for In-house Visits (Visits 3, 4, 5, 6)

Approx. hour	Nominal timing	Activity	Insulin (PK)	Plasma glucose	FFA/ Ketones	Other
Day -1						
CC		Participant arrives at the CRU and continued eligibility will be checked				Weight, height, BMI, physical examination, vital signs, urine pregnancy test, alcohol breath test, eligibility check/ additional exclusion/withdrawal criteria, AEs, concomitant medications
		Randomization (Visit 3 only) Discontinue participant's own insulin pump				
		Start study insulin pump with study intervention (participant's usual basal rate) Insert study CGM system				
		Standardized evening meal Administer individualized bolus dose immediately (0-2 minutes) before dinner meal				CCI
						Overnight stay in CRU with usual overnight basal infusion rates and glucose monitoring with CGM. Morning glucose target CCL mmol/L
Day 1						
CC		Standardized breakfast meal				The meal should be completed within CC Addition of correction bolus with mealtime bolus is allowed, if needed

Approx. hour	Nominal timing	Activity	Insulin (PK)	Plasma glucose	FFA/ Ketones	Other
		Administer individualized bolus dose immediately (0-2 minutes) before breakfast meal				
		Insert venous cannula (arm/hand) for insulin lispro PK, glucose, ketones, and FFA collection prior to lunch				
		Standardized lunch meal Administer individualized bolus dose immediately (0-2 minutes) before lunch meal Set pump to individualized single hourly basal rate	Х	Х		The meal should be completed within CCI Addition of correction bolus with mealtime bolus is allowed, if needed. Collection of PK and glucose prior to meal
			Х	Х	Х	
		Basal rate reduction – 50%	Х	Х	X	For each period, either the 50% or 100% basal
			Х	Х	X	reduction will be used. Depending on the randomization for the participant. Sample collection
		Basal rate reduction – 100%	Х	Х	Х	to occur prior to basal reduction.
		Exercise (treadmill, brisk walking, or jogging at ~45%-55% of predetermined VO 2 peak) x 17 minutes x 3 with two 4-minute and 30-second breaks	Xª	X a	Xa	Heart rate and RPE to be recorded once within each 17-minute interval (within the last 2 minutes of each interval)

Approx. hour	Nominal timing	Activity	Insulin (PK)	Plasma glucose	FFA/ Ketones	Other
						Glucose sampling CCI during exercise period. Samples for FFAs, ketones, and PK will be collected CCI during exercise period

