No additional bolus insulin injection should be administered postmeal after lunch prior to the exercise period. The basal rate will be set to a single hourly rate at lunch based on the participant's usual basal rate for this time of day; this will be maintained until the basal reduction for the exercise period. CC

A cannula will be inserted for venous access for insulin lispro, glucose, free fatty acids (FFA) and ketones sampling at around CCI Based on the randomization, the pump basal rate will be reduced either 60 minutes or 15 minutes prior to the start of exercise period, scheduled for CCI in the following manner:

- 50% basal insulin reduction 60 minutes prior to exercise until end of exercise
- 100% basal insulin reduction 15 minutes prior to exercise until end of exercise CCI

Participants will begin the exercise assessment at approximately 4 hours after lunch (approximately 3 PM). They will be instructed to walk or light jog on the treadmill at approximately 45% to 55% of their predetermined peak VO₂ using three 17-minute intervals with two 4-minute and 30-second rest periods in between the intervals for 1 hour. During this period, samples will be collected for glucose, insulin lispro, ketones and FFAs. Heart rate will be monitored, and participants will be asked to rate their perceived exertion using **CC** scale during the last 2 minutes of each 17-minute interval, as per the assessment day visit. If hypoglycemia ensues (plasma or whole blood glucose level **CC** of oral dextrose.

Upon completion of the exercise period, the pump basal rate will be returned to the participant's usual rate for this time of the day and this basal rate will be maintained until the end of MMTT. Participants will be instructed to rest for approximately 30 minutes.

A standardized liquid dinner MMTT containing approximately **CC** of carbohydrate with a fixed nutrient composition **CC** will be administered approximately hour after the exercise assessment. The same individualized insulin bolus dose determined from the dose assessment will be used for both arms (Lyumjev or Humalog) for all 4 in-house visits, unless it is required to be changed to protect participant safety. The insulin bolus dose will be administered immediately prior (0 to 2 minutes) to the meal using a **CC** minutes.

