9.3 Pharmacokinetic Assessment

9.3.1 Pharmacokinetic Parameter Estimation

The PK analyses will be conducted using standard noncompartmental methods of analysis **CCI** on a computer that meets or exceeds the minimum system requirements for these programs. The version of any software used for the analysis will be documented, and the program will meet the Lilly requirements of software validation. It is possible that other validated equivalent PK software programs may be utilized if appropriate, warranted, and approved by global PK management.

Free serum insulin lispro concentrations will be used to calculate several PK parameters following the meal bolus for the MMTT, including:

• time to early half-maximal drug concentration (early 50% t_{max}),

- time to late half-maximal drug concentration (late 50% t_{max}),
- maximum observed drug concentration (C_{max}),
- time of maximum observed drug concentration (t_{max}),
- AUC from zero to 15 minutes (AUC[0-15min]),
- AUC from time zero to 30 minutes (AUC[0-30min]),
- AUC from time zero to 1 hour (AUC[0-1h]),
- AUC from time zero to 4 hours (AUC[0-4h]),
- AUC from time zero to infinity $(AUC[0-\infty])$.

Other parameters may be calculated as deemed appropriate. Additional partial AUCs may be computed as necessary. If the prebolus insulin lispro concentrations differ between Lyumjev and Humalog prior to the MMTT, the change from baseline values CC

will be used to subtracting the baseline value from all post-dose insulin lispro measurements to calculate the PK parameters. Similarly, the prebolus insulin lispro concentrations differ between Lyumjev and Humalog prior to the lunch before the exercise period, the PK sample collected immediately prior to the bolus will represent as the 0-hour time point for each participant and will be used to subtracting the baseline value from all post-dose insulin lispro measurements to calculate the PK parameters. Other baseline normalization approaches may be explored for assessing the insulin lispro concentrations during the basal reduction. The approach used will be documented in the CSR.

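### The conditional pre-lunch baseline subtraction in SAP 9.3.1 does not suit the basal-reduction and exercise window, where it can distort lispro half-life, AUC and the Lyumjev–Humalog contrast

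*SAP*

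**What the plan says.** SAP 9.3.1 gives two baseline rules for insulin lispro. One concerns the level before the test meal. The other is meant for the case where "the prebolus insulin lispro concentrations differ between Lyumjev and Humalog prior to the lunch before the exercise period". There, "the PK sample collected immediately prior to the bolus will represent as the 0-hour time point for each participant", and it "will be used to subtracting the baseline value from all post-dose insulin lispro measurements to calculate the PK parameters". The SAP gives no criterion for a difference and no rule for zero or negative results. It then adds that "Other baseline normalization approaches may be explored for assessing the insulin lispro concentrations during the basal reduction", with the approach used to be documented in the CSR.

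The timing comes from Protocol 1.3.2 and SAP 5. The sample is scheduled with lunch ("Collection of PK and glucose prior to meal"). The basal rate set at lunch is the participant's usual one, and "this will be maintained until the basal reduction for the exercise period". Exercise follows later: "Participants will begin the exercise assessment at approximately 4 hours after lunch". The cut is either 50% from 60 minutes before exercise or, in the other regimen, "100% basal insulin reduction 15 minutes prior to exercise until end of exercise".

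SAP 9.3.1 next asks for terminal half-life, tlast and AUC(0-tlast) in the suspension period, and for a comparison of the concentration–time profiles. It does not say whether these use measured or subtracted concentrations. SAP 9.3.2 adds an optional untransformed mixed model for exercise PK, with Fieller ratios. Lispro PK during exercise is a listed secondary endpoint (Protocol 3; SAP 4.2).

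**The concern.** Subtracting a baseline isolates a bolus from a background that stays the same. In this window the background is what the trial changes. The pre-lunch value reflects full basal delivery, plus whatever remains of the breakfast bolus, and neither component is constant through the cut.

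Three consequences follow if the rule is applied here. A log-linear half-life changes, because subtracting a constant alters the slope on the log scale. The Lyumjev–Humalog contrast in concentration and AUC shifts, and by construction the rule operates only when the two baselines differ. Values may also reach zero or below, in which case no half-life can be fitted and a Fieller ratio may be unstable because its reference mean is close to zero.

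The clause on other approaches does not settle the matter. It names none and gives no rule for choosing. PK analysis is the sponsor's responsibility (SAP 9.3.1). The sponsor's study team is unblinded and may analyse data while the trial is running (Protocol 4.2 and 9.4). The choice could therefore be made after the data have been seen by treatment.

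**Working it through.** The plan states no figure on this point, so there is none to reproduce.

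**Half-life when values stay positive.** Over an interval T, half-life = T × ln 2 / ln(C1/C2). Take an illustrative fall from 1.4 to 1.1 times the pre-lunch level over 60 minutes.
- Raw: 60 × 0.693 / ln(1.4/1.1) = 41.6 / 0.241 = 172 minutes.
- After subtracting 1.0: 60 × 0.693 / ln(0.4/0.1) = 41.6 / 1.386 = 30 minutes.

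The absolute fall, 0.3, is the same in both. Only the log slope has changed.

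**Contrast.** Let the pre-lunch levels be b_L and b_H. At any time the subtracted Lyumjev–Humalog difference equals the raw difference minus (b_L − b_H). Over a common window of length W, the AUC difference shifts by (b_L − b_H) × W.

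**Sign of the subtracted value.** From the documents: lunch about 4 hours before exercise, 60 minutes of exercise, and the 100% cut from 15 minutes before. At the end of exercise, basal has therefore been off for 75 minutes (1.25 h) and the lunch bolus is 5 hours old. The documents give no lispro half-life and no bolus size. Assumed: half-lives of 40, 60 and 90 minutes, and a lunch bolus equal to 4 or 8 hours of basal. With the steady basal level set to 1, D the bolus in hours of basal and k = ln 2 / half-life per hour:
- lunch tail = D × k² × 5 × exp(−5k)
- model 1: basal remaining = exp(−1.25k), a one-step washout
- model 2: basal remaining = (1 + 1.25k) × exp(−1.25k), which matches the two-step form used for the bolus
- model 3: model 2 plus a breakfast bolus of the same size, assumed 3.5 hours before lunch (its clock time is redacted). It enters both the pre-lunch sample and, at 8.5 hours, the final value.

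Subtracted value = basal remaining + bolus tails − pre-lunch level. For example, model 1 with a 60-minute half-life and D = 4 gives 0.420 + 0.300 − 1 = −0.28.

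| Half-life | Model 1 (D = 4; 8) | Model 2 (D = 4; 8) | Model 3 (D = 4; 8) |
|---|---|---|---|
| 40 min | −0.61; −0.49 | −0.25; −0.13 | −0.65; −0.92 |
| 60 min | −0.28; +0.02 | +0.09; +0.39 | −0.46; −0.71 |
| 90 min | −0.02; +0.41 | +0.31; +0.73 | −0.14; −0.17 |

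The end of exercise is the least favourable time. At the start of exercise, model 1 is positive in all six cases (+0.04 to +0.97). For the 50% regimen at the end of exercise, model 1 gives −0.32 to +0.55.

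A wider grid points the same way. It has 320 scenarios: absorption half-life 45–90 minutes, elimination half-life 15–30 minutes, lunch bolus 3–12 hours of basal, breakfast bolus none or 3–12 hours, and breakfast 3–4 hours before lunch. At the end of exercise 89% (50% regimen) and 93% (100% regimen) of scenarios are negative. Where the two boluses are within two-fold of each other, all are. With no breakfast tail, 44% and 28% stay positive. These are shares of an assumed grid, not probabilities.

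**The case against.** The strongest reply is that the SAP already handles this. The subtraction is conditional, and the sentence after it allows other normalisation during exactly this period. The suspension-period analysis is introduced separately and runs to the last detectable concentration, which is naturally a property of measured values. The exercise model is untransformed and optional, so negative values would not break it. Subtracting one constant per participant and period leaves every fall between time points unchanged.

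Much of that stands, and it rules out three stronger readings that a reader might draw:
- That the rule drives concentrations negative. The documents give no kinetics, and plausible inputs yield either sign.
- That half-lives will be computed from subtracted values and non-positive profiles lost. The SAP does not say which scale it uses.
- That the decline after the cut is erased. Absolute falls survive; log slopes, levels and AUCs do not.

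The reply does not make the text safe. The subtraction is written as applying to all later measurements used for PK parameters, and the alternatives are described only as other approaches that may be explored. It is therefore the stated default for this window, with an undefined trigger and an unnamed replacement.

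**Conclusion.** The point holds as a defect of specification for a secondary endpoint. A baseline taken at full basal rate does not represent the background once basal is cut. Applying it would distort a fitted half-life even with positive values, and would move AUC and the between-insulin contrast by the baseline difference. Those two effects are algebra and need no kinetic assumption; the 172 and 30 minutes are an illustration of scale, not a prediction.

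Zero or negative values by the end of exercise are possible, and are the commoner result in the grid examined, but this rests wholly on assumed half-lives, bolus sizes and breakfast timing. Across the three models the 100% regimen runs from −0.92 to +0.73 of the basal level. Whether the rule reaches the half-life and AUC(0-tlast) at all depends on a trigger and a scale that the SAP leaves open. The primary endpoint, change in plasma glucose, is unaffected.

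**What to change.** In SAP 9.3.1, remove the pre-lunch subtraction for the basal-reduction and exercise window. State that terminal half-life, AUC(0-tlast) and the concentration–time profiles in 9.3.1, and the exercise PK model in 9.3.2, use unsubtracted concentrations for all participants, with no data-dependent trigger.

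If a normalised analysis is wanted, prespecify it as supportive: concentration relative to the participant's own last sample before that period's basal reduction. Note in the SAP that this denominator still contains residual lunch bolus, which may differ between the insulins. Protocol 1.3.2 already schedules sampling before each reduction.

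The cost is SAP wording only, with no new samples or visits. The drawback is that any difference between the insulins in the level before the cut stays in the AUC, so the AUC should be read alongside the pre-cut concentrations. The pre-lunch rule does not appear in Protocol 9.3.3.1, while SAP 11 reports no changes from the protocol; the same revision should update that statement for whatever baseline handling is kept.

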9.3.2 Pharmacokinetic Statistical Methodology

The modified full analysis population will be used for these analyses. The PK parameters for the MMTT and during exercise will be analyzed separately.

During the MMTT

Log-transformed PK parameters AUCs, and C_{max} from insulin lispro during the MMTT will be statistically analyzed using a mixed-effect model. The model will include treatment (Lyumjev or

Humalog) and period as fixed effects, and participant as a random effect. The least squares (LS) means will be back-transformed to produce the treatment geometric LS means, ratio of geometric LS means of Lyumjev to Humalog, and corresponding 90% CIs, as well as the p-value, will be reported.

Example of the SAS code is as follows:

```
proc mixed data=xxx;
  class treat period usubjid;
  model logPK = treat period /residual ddfm=kr;
  random usubjid;
  lsmeans treat / cl pdiff alpha=0.1;
  estimate `Lyumjev vs Humalog' treat 1 -1/ CL alpha=0.1;
  ods output lsmeans=lsm diffs=estims;
run;
```

The same analysis without log transformation will be performed on the PK time parameters (early 50% t_{max} , late 50% t_{max} , and t_{max}) during the MMTT. The treatment LS means, treatment difference in LS means between Lyumjev and Humalog, and corresponding 90% CIs, as well as the 2-sided p-value, will be reported. The treatment ratios and 90% CIs for the ratios will be calculated using the Fieller's theorem³, see Appendix 2 for further details on this calculation.

Statistical significance will be achieved when the p-value for a test is less than 0.10.

During exercise

A mixed-effects model without log transformation that includes treatment (Lyumjev with 50% basal reduction, Lyumjev with 100% basal reduction, Humalog with 50% basal reduction, and Humalog with 100% basal reduction), sequence, and period as fixed effects and participant-within-sequence as a random effect may be used for the exploratory PK endpoints during the exercise period. LS means, treatment differences in LS means, and the corresponding 90% CIs for the treatment differences will be estimated from the model. The p-value on the difference between LS means will be used to determine statistical significance. The treatment ratios and 90% CIs for the ratios will be calculated using the Fieller's theorem (Chow and Liu 2009).

Additionally, exploratory analysis may be conducted if deemed necessary upon review of the data.

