## 9.3.3.2.1. Statistical Analysis of the Secondary PK Endpoints during MMTT

Log-transformed AUCs and  $C_{max}$  for insulin lispro were evaluated to estimate geometric means, ratios of geometric means of insulin lispro within Lyumjev to Humalog, and their corresponding 90% CIs of the ratios using the mixed-effects model that includes treatment (Lyumjev, Humalog) and period as fixed effects and participant as a random effect.

The same model without log transformation was used for the analysis of the PK time parameters (early 50%  $t_{max}$ , late 50%  $t_{max}$ , and  $t_{max}$ ). LSmeans, treatment differences in LSmeans, and the corresponding 90% CIs for the treatment differences were estimated from the model. The 2-sided p-value on the difference between LSmeans was used to determine statistical significance. The treatment ratios and 90% CIs for the ratios were calculated using the Fieller's theorem (Chow and Liu 2009).

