9.5 Exploratory PD Analysis

9.5.1 Continuous Glucose Monitoring

Continuous glucose monitoring data will be collected during the exercise, test meal assessments, and overnight periods (Day -1 from **CCL and and Destination** on Day 1) as both duration (in minutes and percentage of time in range with glucose values between 70 and 180 mg/dL (3.9 and 10.0 mmol/L), inclusive. The parameters to be derived from the CGM data are:

- duration (in minutes) and percentage of time of hypoglycemia with glucose values <54 and <70 mg/dL (3.0 and 3.9 mmol/L)
- duration (in minutes) and percentage of time of hyperglycemia with glucose values >180 and >250 mg/dL (10.0 and 13.9 mmol/L)
- mean glucose
- overall variability (CV and SD)

The parameters will be summarized by treatment and test period (exercise, test meal, in-house period, or overnight), and listed.

The derived CGM parameters will be statistically analyzed for each test period independently using a mixed-effect model. The modified full analysis population will be used for the analysis. The model will include treatment, sequence, and period as fixed effects, and

participant-within-sequence as a random effect. For the in-house and overnight time periods, the categorical variable treatment will have two levels, Lyumjev and Humalog, whereas the exercise and test meal periods will have four levels, Lyumjev with 50% basal reduction, Lyumjev with 100% basal reduction, Humalog with 50% basal reduction, and Humalog with 100% basal reduction. The LS means, difference LS means between Lyumjev and Humalog for corresponding basal rate reduction (test meal and exercise time periods only), difference in LS means between Lyumjev and Humalog (in-house and overnight time periods only), and corresponding 90% CIs, as well as the p-value, will be reported.

If appropriate, the treatment variable for the in-house time period will be changed to use four factors, using the same factors as the test meal and exercise time periods.

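### The two-level product models for MMTT PK and for overnight and in-house CGM carry only a participant intercept and no term for basal-rate reduction, so their 90% CIs are miscalibrated

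*SAP*

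**What the plan says.** - **Sessions.** SAP 5 and 6 define four treatments: A and B are Lyumjev with a 50% and a 100% reduction, C and D are Humalog with the same two. Every participant is randomised to a sequence containing all four, so a completer has two sessions per product.
- **MMTT PK.** Protocol 9.3.3.2.1 specifies a "mixed-effects model that includes treatment (Lyumjev, Humalog) and period as fixed effects and participant as a random effect". The example code in SAP 9.3.2 has "model logPK = treat period /residual ddfm=kr" and "random usubjid", and no other random or repeated statement. CIs are 90% and significance is p < 0.10.
- **CGM.** SAP 9.5.1 states: "For the in-house and overnight time periods, the categorical variable treatment will have two levels, Lyumjev and Humalog". Sequence and period are fixed and the random part is "participant-within-sequence as a random effect". For the in-house period alone there is an option: "If appropriate, the treatment variable for the in-house time period will be changed to use four factors". No criterion for using it is given.
- **Reduction.** The reduction level enters neither the MMTT PK model nor the two-level CGM models. Protocol 1.3.2 places the overnight stay at the usual basal rate, before any reduction.

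**The concern.** With product as a two-level factor and a participant intercept as the only random term, a participant's two sessions on one product are treated as independent replicates of the product effect. Any true difference between participants in the Lyumjev-to-Humalog contrast goes into the residual, where it is averaged with within-product variation. The same residual also absorbs any effect of the reduction level. These two omissions push the standard error in opposite directions, and nothing in the plan makes them balance.

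At stake are the CIs and p-values for insulin lispro PK in the MMTT, which is a stated secondary objective, and for the exploratory overnight and in-house CGM contrasts. All are judged at a 10% level with no multiplicity adjustment (protocol 9.1.1).

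**Working it through.** **Inputs.** 28 completers (SAP 7); sequences ADBC, BACD, CBDA, DCAB (SAP 6); two-sided alpha 0.10 (SAP 9.3.2). The only planned precision figure in the documents is the sample size for the primary endpoint. A paired t-test with SD 27.9 and difference 14 mg/dL gives 82.7% power at n = 28 (80.1% at n = 26), so the stated 80% is roughly reproduced. It says nothing about PK or CGM. The SDs below are therefore **assumptions, shown as a range**.

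**Notation.** σ_e is the session SD. σ_D is the SD between participants of the true Lyumjev-minus-Humalog effect. d is the difference between the two reduction levels. For AUC and C_max these are on the log scale. With d = 0 only the ratio σ_D/σ_e matters.

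**Step 1: true variance.** A participant's mean Lyumjev minus mean Humalog has variance σ_e²/2 + σ_e²/2 + σ_D² = σ_e² + σ_D². The estimate over n participants has variance (σ_e² + σ_D²)/n.

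**Step 2: variance the model uses.** Four sessions give three within-participant contrasts: product, reduction and their interaction. Their expected mean squares are σ_e² + σ_D², σ_e² + d² and σ_e². The intercept-only model pools them, so it uses about [σ_e² + (σ_D² + d²)/3]/n. The residual df are 112 − 28 − 3 − 1 = 80. Kenward-Roger cannot restore a variance component that is not in the model.

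**Step 3: no reduction effect (d = 0).** The ratio of true to model variance is (σ_e² + σ_D²)/(σ_e² + σ_D²/3). The approximate rejection rate is 2·P(t₈₀ > 1.664/√ratio).

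| σ_e | σ_D | True | Model | Ratio | Type I, formula | Type I, simulated |
|---|---|---|---|---|---|---|
| 0.20 | 0 | 0.0400 | 0.0400 | 1.00 | 10.0% | about 10% |
| 0.20 | 0.10 | 0.0500 | 0.0433 | 1.15 | 12.5% | 12.6% |
| 0.20 | 0.15 | 0.0625 | 0.0475 | 1.32 | 15.1% | 15.0% |
| 0.20 | 0.20 | 0.0800 | 0.0533 | 1.50 | 17.8% | 17.6% |
| 0.20 | 0.25 | 0.1025 | 0.0608 | 1.69 | 20.4% | 20.8% |
| 0.30 | 0.10 | 0.1000 | 0.0933 | 1.07 | 11.2% | 11.1% |
| 0.30 | 0.15 | 0.1125 | 0.0975 | 1.15 | 12.5% | 12.7% |
| 0.30 | 0.20 | 0.1300 | 0.1033 | 1.26 | 14.2% | 14.4% |
| 0.30 | 0.25 | 0.1525 | 0.1108 | 1.38 | 16.0% | 16.4% |

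The simulation used the SAP sequences and complete data, where the within-participant least-squares fit gives the same product contrast as the random-intercept model.

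**Step 4: with a reduction effect.** Take σ_e = σ_D = 0.20, so the true variance is 0.0800.

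| d | Model | Ratio | Type I, formula |
|---|---|---|---|
| 0 | 0.0533 | 1.50 | 17.8% |
| 0.2 | 0.0667 | 1.20 | 13.3% |
| 0.3 | 0.0833 | 0.96 | 9.3% |
| 0.4 | 0.1067 | 0.75 | 5.8% |

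Simulation gave 13.4%, 8.9% and 5.6% for the last three. The two errors cancel when d² = 2σ_D², here |d| = 0.28. Participant-by-reduction variation offsets in part as well: with its SD equal to σ_D, 18.2% falls to 13.3%.

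**Step 5: which analyses have the offset.** The MMTT follows the reduction and the in-house CGM window contains it, so step 4 applies to both. The overnight window precedes it, so d = 0 and step 3 applies unmodified.

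**The case against.** **A random-intercept crossover model is a standard specification, and the size rests on quantities the documents do not give.** Both statements are correct. With σ_D = 0 there is no inflation from this source, and at the low end of the range it is one to three points. The top of the range needs a product-effect SD larger than the session SD.

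**The intervals may not be too narrow at all.** A reader might infer from the missing participant-by-product term that every one of these CIs is anti-conservative. The documents do not support that for MMTT PK or in-house CGM, because the omitted reduction effect can cancel or reverse the error (step 4). This objection stands in full, and the point is therefore miscalibration, not a uniform bias. It does not reach overnight CGM.

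**The MMTT PK model might be run within each reduction level.** Protocol 9.3.3.2 speaks of comparisons under either reduction, and the SAP code is labelled an example. Run separately, each participant would have one session per product and an intercept would suffice. But SAP 9.3.2 gives treatment two product levels for the MMTT and, in the same section, four product-by-reduction levels for exercise. It mentions no split by reduction for the MMTT.

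**In-house CGM may move to four levels.** That lessens the problem without removing it. For a product difference within one reduction, with q = σ_D²/σ_e², the ratio is (1 + q/2)/(1 + q/3): 1.125 at q = 1 and at most 1.5. The option does not extend to overnight CGM or MMTT PK.

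**Some participants may contribute a single product pair.** SAP 8 admits them to the modified full analysis set. They reduce the replication and so the size of the effect.

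**Conclusion.** The point holds as a conditional one. The three two-level analyses use a standard error that ignores variation of the product effect between participants, and in two of them the standard error also absorbs the reduction effect. For overnight CGM the CIs are too narrow whenever such variation exists. For MMTT PK and in-house CGM they may be too narrow or too wide, depending on how d compares with 1.41·σ_D. Under the assumed SDs with no reduction effect, the nominal 10% test runs at about 11% to 20%, which is coverage of about 89% down to 80% for a nominal 90% CI.

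The scope is one secondary PK family and exploratory CGM. A reader might extend the point to the primary endpoint. It does not carry over: SAP 9.4.2 gives that model four product-by-reduction levels and compares products within each reduction, so it is not one of the two-level models examined here.

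**What to change.** - In the MMTT PK code and the two-level CGM models, specify `random usubjid usubjid*treat;` (nested in sequence for CGM), state Kenward-Roger df, and keep period as a fixed effect.
- For MMTT PK and in-house CGM, add basal-rate reduction (50%/100%) as a fixed factor. The random term alone is not enough: if a large reduction effect stays in the residual, REML can set the new variance component to zero and the CI stays too wide. Overnight CGM does not need this factor.
- If participant-level product differences are analysed instead, adjust them for sequence. Product order differs between sequences, so an unadjusted paired t-test lets period effects into the differences. With a trend of 0.1 per period and no heterogeneity, its type I error was 3.6% and its CIs were 31% wider than those of the SAP model. The sequence-adjusted version (24 df) kept coverage at 89.6% to 90.3% over all the heterogeneity settings simulated.

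**Cost.** A small change to the model code. With no heterogeneity the CI widens by about 2% to 3%: t rises from 1.664 (80 df) to 1.703 (27 df, 1.703/1.664 = 1.023) or 1.711 (24 df, 1.028). With heterogeneity and d = 0 the extra width is the correction itself: √1.071 × 1.023 = 1.06 at the mildest setting in step 3 with σ_D above zero, and √1.685 × 1.023 = 1.33 at the strongest. Where a reduction effect now inflates the residual, modelling it can make the CI narrower.
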